9.2.4.8. Hospitalization or Prolonged Hospitalization

The following hospitalizations are not considered SAEs in this clinical trial:

- Admissions per protocol for a planned medical/surgical procedure. Planned hospital admissions or planned surgical procedures for an illness or disease that existed before the patient was enrolled in the trial or before study drug was given are not to be considered AEs, unless they occur at a time other than the planned date for a reason such as a worsening of the underlying disease/illness/symptoms.
- Routine health assessment requiring admission for baseline/trending of health status (e.g., routine colonoscopy).
- Medical/surgical admission for purpose other than remedying ill health state and was planned prior to entry into the study. Appropriate documentation is required in these cases.

Admission encountered for another life circumstance that carries no bearing on health status and requires no medical/surgical intervention (e.g., lack of housing, economic inadequacy, care-giver respite, family circumstances, administrative).

9.2.4.9. Pregnancy Exposure and Birth Events Reporting

Andexanet is not expected to have reproductive or developmental toxicity based on the following:

- Andexanet is intended for single-dose administration and, therefore, has limited potential for reproductive or developmental toxicity.
- Andexanet is a biotechnology-derived protein that is a modification of an endogenous protein in the coagulation cascade (FXa).
- Andexanet has a very short $t_{1/2}$ (1–2 hour effective $t_{1/2}$).
- Andexanet was designed as a universal antidote for FXa inhibitors, which are prescribed primarily in elderly patient populations that are not of reproductive capacity.

However, it is recommended that women of childbearing potential must use highly effective methods of contraception through at least 1 month following study drug dose. Additionally, men with sexual partners of childbearing potential must use highly effective methods of contraception for the entire duration of the study and for at least 1 month following study drug and must refrain from attempting to father a child or donating sperm in the month following the administration of study drug. The definition of highly effective methods of contraception follow the Clinical Trial Facilitation Group recommendations [31].

Periodic abstinence (e.g., calendar, ovulation, symptothermal, post-ovulation methods) and withdrawal are not acceptable methods of contraception.

If a female study patient becomes pregnant or a female partner of a male study patient suspects she is pregnant, the Investigator should be informed immediately. The Sponsor must, in turn, also be notified by the Investigator immediately by completing a Pregnancy Form. If a female partner of a male study patient is pregnant or suspects she is pregnant, the male patient will be advised by the study Investigator to have his pregnant partner inform her treating physician immediately. The pregnancy must be followed up through delivery or other fetal outcome and information reported on a Pregnancy Follow-up form. For any abnormal fetal outcome (including congenital anomaly or birth defect, spontaneous or therapeutic abortion, still birth, pre-mature birth, or other outcome other than live normal birth), the Investigator should promptly report the abnormal fetal outcome to the Sponsor on an SAE form.

10.0 STUDY ASSESSMENTS

Assessments, testing, and treatment schedules are detailed in [Appendix A](#). No reference to timing or frequency is described below.

10.1. Baseline Assessments

10.1.1. Informed Consent

An IRB/EC approved informed consent will be administered prior to performing study specific procedures or assessments. Administering informed consent is a process and will be documented in source documents. The current IRB/EC version of the consent will be used. See Section [13.2](#) for additional details on informed consent procedures.

10.1.2. Demographics

Demographics will record the age, sex, race, and ethnicity of patients. Race will be recorded (American Indian or Alaska Native, Asian, Black or African American, Native Hawaiian or Other Pacific, White), and ethnicity will be recorded as Hispanic or Latino or Non-Hispanic or Latino.

10.1.3. Medical History

Patients will have a detailed medical history completed as part of baseline assessments. Diagnosis, year of onset and status will be reported. Status will consist of an end date or documentation as ongoing for the condition. Diagnosis should be documented and not signs and symptoms. Events with current treatment will have the treatment recorded in concomitant medications and therapies.

10.1.4. Prior and Concomitant Medications

Patients will be asked about their current physician prescribed medications, over the counter medications and any herbal or nutritional supplements. The generic name is preferred for Electronic Data Capture (EDC) entry. The dose, posology, frequency, start and stop dates and the diagnosis for use will be recorded.

10.1.5. Anticoagulant Dose or Plasma Level

Patients will be asked about the brand, dose and time of last dose of their anticoagulant. For patients who received the last dose of FXa inhibitor more than 15 hours (or an unknown time) prior to start of surgery, a local anti-fXa activity level may be obtained to allow enrollment of patients with >100 ng/mL levels. See Section [10.2.1](#) below on details for this local testing.

10.1.6. American Society of Anesthesiologists Physical Status Classification (ASA PS)

The American Society of Anesthesiologist Physical Status Classification is used to evaluate and describe the general health of patients prior to use of anesthetics or prior to surgery. The ASA PS consists of 6 categories to describe a patient's physical status ([Appendix F](#)). It will be used to describe the population enrolled in the trial. It is not an assessment of operative risk, and will not be repeated during the study.

10.1.7. Eligibility Assessment

Following completion of assessments and screening testing, the investigator will determine eligibility of the patient by comparing results to inclusion and exclusion criteria. Note: It is the Sponsor's policy not to grant exceptions or waivers for inclusion and exclusion criteria.

10.1.8. Patient Identification Numbers

Patients will be considered to be in Screening once they have signed the ICF. At this time, patients will be assigned a patient identification number. Patients will be considered to have enrolled in the study once they have signed informed consent and met the inclusion and exclusion criteria.

10.2. Central Laboratory Testing

Samples will be taken for analysis at central laboratories to assess biomarkers informing on both safety and efficacy and include samples for the assessment of the following: anti-fXa and anti-IIa activity, TG, TFPI and immunogenicity. Specific guidance for the collection, processing, and storage of specimens for each biomarker will be described in the Laboratory Manual provided to each site. The site initiation visit will include training on the collection, processing, and storage of the samples.

Samples for analysis at central laboratories will be processed (generally to plasma) and stored frozen until shipment to a central location for distribution to the specific laboratory that conducts each type of analysis. Samples will be analyzed only for the biomarker described in the ICF and herein. Samples will be maintained in accordance with all regulatory guidance. At the end of the study conduct and completion of the clinical study report (CSR), samples will be maintained for re-analysis at regulatory request for as long as the biologic viability of the sample has been demonstrated. Once regulatory authorities have had the opportunity to review the CSR and the Sponsor believes that there are unlikely to be questions regarding the specific samples, they will be destroyed in accordance with Good Laboratory Practice guidance and appropriate regulations.

10.2.1. Anti-fXa Activity

Anti-fXa activity will be measured using plasma samples to assess the ability of andexanet to reverse the anticoagulant effect of FXa inhibitors. Anti-fXa activity will be measured by a modified chromogenic assay. These assays will be performed at a Central Laboratory.

Local laboratory anti-fXa activity testing may be utilized additionally by sites to ascertain eligibility (> 100 ng/ml) if the time of last dose of FXa inhibitor is greater than 15 hours (or unknown). Local laboratory testing post-andexanet administration should be done with caution due to potential invalidity of local lab results from excessive sample dilution.

10.2.2. Thrombin Generation

Thrombin generation will be measured using plasma samples to assess the ability of andexanet to reverse the anticoagulant effect of FXa inhibitors. Thrombin generation will be measured using a tissue factor (TF)-initiated TG assay. This assay will be performed at a Central Laboratory. Five parameters related to TG are measured: endogenous thrombin potential (ETP), peak height, time to peak height, lag time and velocity index. Endogenous thrombin potential is prospectively identified as the primary measure for TG.

10.2.3. Tissue Factor Pathway Inhibitor

The TFPI activity will be measured using plasma samples in a Central Laboratory using a validated assay. The TFPI functional activity will be determined using a commercial kit. The assay measures FXa chromogenic activity following FX activation by factor VIIa/TF added to the plasma. The TFPI activity is quantified by using a TFPI standard with U/mL as the readout. Binding of andexanet to TFPI will reduce the TFPI activity readout.

10.2.4. Anti-IIa Activity

Anti-IIa activity levels will be measured in patients taking enoxaparin using plasma samples. Anti-IIa activity will be measured using a modified chromogenic assay. Anti-IIa activity results will be performed in a Central Laboratory.

10.2.5. Antibody Testing

Determination of the possible presence of antibodies to FX (human) and FXa (human) will be done at specific time points (see [Appendix A](#)) using the modified Bethesda assay. Antibodies against andexanet and HCPs will be assessed using standard immunogenicity assays.

For any sample that is positive for antibodies against andexanet, the potential for nAb activity will be further assessed by measuring the functional activity of andexanet in plasma. These tests will be performed by a Central Laboratory.

10.3. Safety Assessments (other than Adverse Events)

10.3.1. Vital Signs

Vital signs include temperature ($^{\circ}\text{C}$), systolic blood pressure (SBP) (mmHg), diastolic blood pressure (mmHg), heart rate (beats per minute), and respiratory rate (respirations per minute).

10.3.2. Physical Examination

A physical examination will be performed on all patients at various time points before and after the surgical procedure. The examination will include, at a minimum, any component relevant to the indication for surgery (e.g., abdominal examination for appendicitis, hip examination for hip fracture, neurologic examination for spinal cord compression) and an assessment of the surgical incision site (post-operative only).

10.3.3. Weight

Patient weight will be recorded in kg according to the schedule of assessments in [Appendix A](#).

10.3.4. Clinical Laboratory Testing

Blood specimens for routine chemistry and hematology will be obtained at selected time points (see [Appendix A](#)).

The following assays will be performed at the Local Laboratory:

- Hematology: hemoglobin, hematocrit, white blood cell (WBC) count, platelet count, WBC differential.
- Coagulation: prothrombin time reported as the INR.
- Serum Chemistry: sodium, potassium, chloride, carbon dioxide (bicarbonate), glucose, blood urea nitrogen, creatinine, aspartate aminotransferase, alanine aminotransferase, alkaline phosphatase, and total, direct, and indirect bilirubin.
- Serum or urine pregnancy test (in women of child bearing potential; see [Appendix D](#)).

10.3.5. Optional Local Laboratory Testing of Anti-fXa Levels

Local laboratories may perform tests to evaluate anti-fXa activity to address inclusion criteria. Further details and guidance on the conduct of local laboratory anti-fXa assays can be found in the Laboratory Manual for ANNEXA-S. Investigators are discouraged from evaluating anti-fXa activity with local assays after the administration of andexanet, due to the known inaccuracy of post-andexanet results caused by the large sample dilutions associated with unmodified commercial anti-fXa assays; however, if such testing is deemed necessary, it is strongly recommended that the procedures outlined in the Laboratory Manual be followed.

10.4. Intraoperative and Hospitalization Assessments

10.4.1. Surgical Intervention

All patients entering the trial are required to have an urgent need for surgical intervention. Institutional or procedural consents should be administered for the surgical intervention in accordance with local requirements and in addition to the study specific informed consent.

- The start of surgery is the initial incision.
- The end of surgery is final skin closure. If skin closure is not completed by intention, an equivalent milestone such as dressing or packing the surgical incision may be considered the end of the procedure.

10.4.2. Intraoperative Blood Loss

Investigators will report predicted blood loss and observed blood loss during surgery for each patient. Predicted blood loss must be determined by the investigator prior to the first incision. Observed blood loss will be reported as an estimate of blood loss in milliliters at the end of surgery. It is an intraoperative assessment and will not be updated for post-closure blood loss. Observed blood loss will be measured against predicted blood loss.

10.4.3. Assessment of Intraoperative Hemostasis

Intraoperative hemostasis will be captured as an investigator assessment. Categories for assessment are provide in [Table 3](#) (Section 11.5.1).

10.4.4. Blood Products and Hemostatic Treatments

Blood products and hemostatic treatments employed as treatment prior to, during and postoperatively will be recorded. The product (generic), dose, route of administration, date and time of use will be recorded along with the reason for use.

10.4.5. Bleeding-related Diagnostic and Therapeutic Procedures

Any diagnostic and/or therapeutic procedures employed prior to, during and postoperatively will be recorded. For diagnostic procedures, the procedure, date, time, results and relevant units or description of results will be captured. Therapeutic procedures will be captured and concomitant medications/treatments with date, time, and posology (if applicable).

As a concomitant treatment, Investigators will record the product (generic name), date, time, indication, and posology of colloid or crystalloid treatments used to support hemodynamic status.

10.4.6. Record Hours in Hospital Care Units

Investigators will record the date and time of entry into each care unit of the hospital. The date and time of entry and exit for each unit will be reported. This will be locally variable, but categories should be reconciled to the standards below:

- Emergency Department (ED): a unit dedicated to medical and surgical patients in need of immediate care.
- Intensive Care/Critical Care Department (ICU): a specialty medical unit for patients that are seriously ill are maintained under constant medical observation.
- Operating Room (OR): the room where the surgical procedure actually takes place.
- Post-anesthesia Care Unit (PACU): a specialty unit for providing post-anesthesia care for patients recovering from anesthesia.
- General Hospital Department or General Surgical Department: Covers a wide range of types of surgery and procedures on patients.

10.5. End of Study Assessments

Patients will have their survival status reported by phone on the Day 30 or End of Study visit. This assessment will record the patient's status as alive or provide the date, time, and cause of death. Note: see Section 9.0 for AEs reported for all deaths.

11.0 STATISTICAL CONSIDERATIONS AND DATA ANALYSIS

The study objectives and study design are described in Sections [2.0](#) and [3.1](#), respectively. The information in this section is a summary of the planned statistical analyses. Further details will be provided in the Statistical Analysis Plan.

11.1. General Considerations

Statistical summaries will be performed using SAS Version 9.4 (SAS Institute, Inc., Cary, NC, USA) or higher. Additional software may be used for the production of graphics and for statistical methodology not available in SAS.

Unless otherwise specified, all confidence intervals (CIs) will be 2-sided and reported at the 95% confidence level.

11.2. Randomization

This is a prospective, open-label study with a single treatment arm. Consequently, there is no randomization.

11.3. Analysis Populations

11.3.1. Enrolled Population

The enrolled population will consist of all patients enrolled (signed informed consent and met inclusion/exclusion criteria) into the study irrespective of whether they received andexanet or not.

11.3.2. Safety Analysis Population

The safety analysis population will consist of all patients enrolled and treated with any amount of andexanet. All safety analyses will be based on the safety analysis population.

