Amendment 2.2 (Japan) 30 AUG 2021

Overall Rationale for the Amendment:

Update necessitated from reconsideration of andexanet dosage in edoxaban 15-30 mg treated Japanese patients. High-dose andexanet will be administered to these patients.

Section # and Name	Description of Change	Brief Rationale
PROTOCOL SYNOPSIS Test Product, Dose, and Mode of Administration	Changed andexanet alfa dose in Edoxaban 15-30 mg treated patients. <Amendment 2.1 (Japan)> Last dose of FXa inhibitor: < 8 hours - Edoxaban 15-30 mg (ONLY for VTE prophylaxis for patients undergoing orthopedic surgery of the lower limbs): Low dose andexanet alfa - Edoxaban 30 mg-60 mg: High dose andexanet alfa <Amendment 2.2 (Japan)> Last dose of FXa inhibitor: < 8 hours - Edoxaban 15 mg-60 mg: High dose andexanet alfa	In study 16-508, there was no statistically significant difference in the reduction in anti-fXa activity between the andexanet low dose group and placebo group in healthy Japanese subjects who took 30 mg of edoxaban. Therefore, in edoxaban 15-30 mg treated patients, high-dose andexanet is considered to ensure the reversal effect without any specific risk. Thus, the andexanet dose changed to high dose.
6.2 Dosing and Administration Table 2	Same as above	Same as above
9.2.2. Assessment of Causal Relationship	Deleted.	Deleted due to the Administrative Change Letter on 01APR2021.

Amendment Rationale:

The amendment is prepared for executing the study under the regulatory requirements and medical practice in Japan. This country-specific amendment changed a part of the protocol contents and applies to all subjects enrolled in Japan.

Changes to the Protocol:

Page	Protocol Section	Revised Protocol Text																	
22	PROTOCOL SYNOPSIS Test Product, Dose, and Mode of Administration	Revised, deleted, and Added the following underlined parts.																	

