4.2. Exclusion Criteria

If a patient meets any of the following criteria, he or she is *not* eligible to participate:

1. Surgery for which the risk of clinically meaningful uncontrolled or unmanageable bleeding is low.
2. Acute life-threatening bleeding (ISTH criteria [32]) at the time of Screening:
 - a. The patient has acute-overt bleeding that is potentially life-threatening, e.g., with signs or symptoms of hemodynamic compromise, such as severe hypotension, poor skin perfusion, mental confusion, low urine output that cannot be otherwise explained.
 - b. The patient has overt bleeding associated with a fall in hemoglobin level by ≥ 2 g/dL, OR, a hemoglobin ≤ 8 g/dL if no baseline hemoglobin is available.
 - c. The patient has acute bleeding in a critical area or organ, such as pericardial, intracranial, or intraspinal.

3. Any surgical procedure that involves the intraoperative use of systemic, intravascular, unfractionated heparin.
4. Primary procedure being considered for efficacy evaluation is a non-surgical interventional procedure (e.g., skin biopsy, lumbar puncture, cardiac catheterization, endoscopic retrograde cholangio-pancreatography).
5. Expected survival of < 1 month due to comorbidity.
6. Known “Do Not Resuscitate” order or similar advanced directive.
7. The patient has a recent history (within 30 days prior to Screening) of a diagnosed TE as follows: VTE (including DVT, PE, intracardiac thrombus); MI (including asymptomatic troponin elevations); disseminated intravascular coagulation (DIC); acute traumatic coagulopathy; cerebrovascular accident; transient ischemic attack; unstable angina pectoris hospitalization; or severe peripheral vascular disease (see [Appendix B](#) for DIC scoring algorithm).
8. Acute decompensated heart failure or cardiogenic shock at the time of screening (see [Appendix C](#) for cardiogenic shock definition).
9. The patient has sepsis or septic or hemorrhagic shock at the time of Screening (see definition in Appendix C).
10. The patient has heparin-induced thrombocytopenia (with or without thrombosis).
11. Inherited coagulopathy (e.g., anti-phospholipid antibody syndrome, protein C/S deficiency, Factor V Leiden) at time of Screening.
12. Platelet count < 80,000/ μ L at the time of Screening.
13. Last dose of apixaban < 2.5 mg, rivaroxaban < 10 mg, edoxaban < 30 mg, enoxaparin < 40 mg.
14. The patient is pregnant or a lactating female.

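### The Safety Analysis Population requires patients to be enrolled, and enrolled means eligibility criteria met; read literally, a dosed patient who failed a criterion is left out of the planned safety summaries

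*Protocol*

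**What the plan says.** Section 11.3.2 sets two conditions for the safety set, enrolment and exposure: "The safety analysis population will consist of all patients enrolled and treated with any amount of andexanet". It then ties every planned safety analysis to that set: "All safety analyses will be based on the safety analysis population". Section 11.7 repeats that the safety endpoints are analysed there.

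Enrolment is defined twice, in the same terms. Section 11.3.1 describes the Enrolled Population as "all patients enrolled (signed informed consent and met inclusion/exclusion criteria) into the study irrespective of whether they received andexanet or not". Section 10.1.8 says: "Patients will be considered to have enrolled in the study once they have signed informed consent and met the inclusion and exclusion criteria". Section 10.1.7 says who decides: after the screening assessments, "the investigator will determine eligibility of the patient by comparing results to inclusion and exclusion criteria".

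Nothing in the protocol text available says what happens to the population membership of a patient who is dosed and then proves not to have met a criterion. The statistical analysis plan was not available for this check. The definition is, however, fixed in the protocol itself: a plan that repeats it would carry the same problem, and one that departs from it would contradict the protocol.

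**The concern.** A safety set is normally defined by exposure alone, so that no patient who received the drug can leave the denominator because of something learned about the patient afterwards. Here a second condition has been added, and it depends on facts that may be settled or corrected only after dosing. This is a single-arm study of about 100 patients. Thrombotic events and deaths are key safety outcomes, and no control group would absorb or reveal a distortion, so a handful of patients matters.

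It matters most for the thrombosis-related exclusions. Section 3.5 justifies excluding patients with a recent thrombotic event, a hypercoagulable state or recent procoagulant treatment by their markedly raised thrombotic risk. If such a patient is dosed in error and then has an event, a literal reading removes that event from the summary where it is most relevant.

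**Working it through.** **1. The definitions chained together.** Safety set = enrolled AND treated (11.3.2). Enrolled = consented AND criteria met (11.3.1, 10.1.8). Therefore safety set = consented AND criteria met AND treated. A patient who was treated but did not meet a criterion is not in it.

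**2. Whether such patients can arise.**
- Inclusion criterion 4a (Section 4.1) sets a limit of 15 hours from the last factor Xa inhibitor dose to the start of surgery. The alternative, 4b, needs a local anti-fXa result above 100 ng/mL (0.5 IU/mL for enoxaparin) obtained within 2 hours before consent. Criterion 3 concerns surgery within 12 hours of consent.
- Section 6.2 requires the bolus to be complete before incision. Dosing therefore comes before the event against which 4a is measured. If incision slips past the limit, or the operation is cancelled, the criterion can fail after exposure. Section 11.6 lists cancelled surgeries among the expected losses.
- Under Section 10.1.5 the brand, dose and time of the last anticoagulant dose come from asking the patient, and such details can be corrected later.
- Exclusion 7 covers a thrombotic event diagnosed in the 30 days before screening. Records obtained after dosing can show one that the site did not know about.

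**3. The plan's own figure.** The only planning figure is the precision of the primary efficacy proportion: 100 × (1 − 0.20) = 80 evaluable patients, with a 95% half-width below 11%. At the worst case p = 0.5, 1.96 × √(0.25/80) = 10.96%, so it is reproduced. It does not depend on the safety definition.

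**4. Illustration of size.** The protocol gives no expected number of treated but ineligible patients, so the counts below are assumptions. Take 100 treated and 10 with a thrombotic event: 10/100 = 10.0% (exact 95% CI 4.9% to 17.6%). If d patients are dropped and k of them had an event, the reported rate is (10 − k)/(100 − d).

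| Dropped (d) | Events among dropped (k) | Reported rate |
|---|---|---|
| 2 | 0 to 2 | 10/98 = 10.2% down to 8/98 = 8.2% |
| 5 | 0 to 5 | 10/95 = 10.5% down to 5/95 = 5.3% |
| 10 | 0 to 5 | 10/90 = 11.1% down to 5/90 = 5.6% |

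With 10 dropped and 1 event among them, the rate is 9/90 = 10.0%, with no change.

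**5. Direction.** Let f be the ineligible fraction of treated patients, rE the event rate in the eligible and rI the rate in the ineligible. The all-treated rate is (1 − f)rE + f·rI and the reported rate is rE, so the error is f(rE − rI). Take rE = 9.7%, the thrombotic event rate in the earlier bleeding study (Section 1.4.7), and assume f = 10%:
- rI = 20% (assumed): all-treated 0.9 × 9.7% + 0.1 × 20% = 10.7%, so 9.7% is about 1.0 point too low. At f = 5% and 15% the all-treated rates are 10.2% and 11.2%.
- rI = 5% (assumed): all-treated 0.9 × 9.7% + 0.1 × 5% = 9.2%, so 9.7% is about 0.5 point too high.

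The sign is decided entirely by whether rI exceeds rE.

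**The case against.** The best defence is that enrolment is a status reached once, when the investigator judges eligibility at screening. Section 10.1.8 speaks of the moment when the conditions have been met, Section 10.1.7 makes eligibility the investigator's decision, and no provision removes a patient from enrolment afterwards. Section 13.6 deals with non-compliance as a protocol deviation, and Section 4.4 asks for full safety follow-up of anyone who leaves after receiving any andexanet. This reading is reasonable and may be what the sponsor intends. But the protocol does not state it. Both definitions turn on criteria having been met, not on having been judged met, and the safety denominator should not depend on which reading is programmed.

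Other parts of the defence stand and limit the point:
- Several exclusions are tied to the time of screening or to what is known, and exclusion 7 to a diagnosed event. A condition first diagnosed after dosing does not clearly breach them.
- The bolus starts at most 30 minutes before the planned incision, so timing failures after dosing should be few.
- Reporting of serious adverse events and thrombotic events (Section 9.2.1), adjudication for all patients and Board review of all safety data (Section 12.0) do not depend on the safety set. A reader might infer that these patients go unreported or unmonitored; the documents do not support that.
- A reader might also infer that the bias always flatters the drug. It does so only if the dropped patients are at higher risk. Section 3.5 supports that for the thrombosis-related exclusions, but low-bleeding-risk surgery, a low inhibitor dose or a missed time limit do not by themselves mark thrombotic risk.
- The Japan edoxaban row does not show that the plan itself produces ineligible treated patients. A dosing row confers no eligibility, and Section 10.1.7 rules out waivers.

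**Conclusion.** The point holds as a defect in a stated definition. Read literally, Section 11.3.2 together with 11.3.1 and 10.1.8 leaves a treated patient who did not meet a criterion out of all planned safety summaries, and no text available puts that patient back. The consequence is confined to the analysis tables.

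Neither the size nor the direction can be determined from the protocol. The 5.3% to 10.5% range around 10.0% assumes 100 treated, 10 events and 5 dropped, and its lower end requires all 5 to have had an event. Either end lies inside the exact interval for 10/100, so the effect may be modest beside sampling error. Unlike sampling error, though, it is avoidable.

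**What to change.** Reword Section 11.3.2 so that the Safety Analysis Population is every patient who received any amount of andexanet, whether or not the eligibility criteria were met. This is one line. It needs no new data, alters no sample-size or precision figure, and has no real downside. If the sponsor already treats enrolment as fixed at screening, the change simply says so.

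Whether the Efficacy Analysis Population in Section 11.3.3 should also disregard eligibility failures is for the sponsor. It is a separate choice with a possible cost, since admitting low-bleeding-risk operations could raise the apparent rate of effective hemostasis.

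As a separate item, the Japan amendment's dosing row ("Edoxaban 15 mg-60 mg: High dose andexanet alfa") must be reconciled with inclusion criterion 4, which requires a last edoxaban dose of at least 30 mg, and with exclusion criterion 13 ("Last dose of apixaban < 2.5 mg, rivaroxaban < 10 mg, edoxaban < 30 mg, enoxaparin < 40 mg"). The changes listed for Amendment 2.2 do not touch eligibility. The Amendment 2.1 change list could not be read in full.
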